These approaches are expected to enhance the therapeutic benefit of immune checkpoint inhibitors by bypassing issues of local immune tolerance. However, with the exception of treatment strategies that directly target melanoma (e.g. MAPK inhibitors) immunotherapeutic-based strategies are not expected to have an effect, if melanomas are not immunogenic⁵². Based on the estimate from TCGA in cutaneous melanomas, lack of immunogenicity is seen in up to 50% of cutaneous melanoma cases¹³. Cancer immunogenicity and antigenicity is a complex phenomenon that dynamically changes as cancers develop, establish and progress. While during early stages of cancer development both immunoreactive and non-immunoreactive tumor clones may be present, the process of cancer immunoediting may gradually eliminate the former whereas the latter may be left unchecked and grow⁵³. Another important issue is that immunogenicity and antigenicity are not strictly dependent on the number of somatic mutations, although admittedly various studies have shown a moderate but significant benefit from immune checkpoint inhibitors in patients with high neoantigen burden and across various cancers⁵⁴. There is a growing number of reports that resistance to various FDA-approved treatments in metastatic melanoma –both targeted therapies and immunotherapies– is also transcriptionally/epigenetically mediated⁵⁵. Therefore, it is tempting to speculate that **drugs which affect transcription may potentially render less immunoreactive tumors to more immunoreactive.**

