1.7 Correlative Studies

The study contains a single integral tumor tissue biomarker and several exploratory tumor tissue and peripheral correlative biomarkers.

1.7.1 Integral Biomarker. Assessment of TIL/TAL in representative H&E-stained sections from archived tumor tissues to determine eligibility for the trial during screening.

Since the primary endpoint of the study is to assess the incidence of conversion of non-inflamed vs. inflamed melanoma following 3 weeks of entinostat monotherapy, we will use a cost-efficient assay to determine eligibility, namely assessment of TIL/TALs in archived metastatic melanoma specimens. Since the presence of TIL/TALs can be heterogeneous within the same tissue as well as across different metastatic sites, the following are requirements for archived tumor tissue eligibility:

- The amount of surface area corresponding to melanoma devoid of stroma should be at least 1cm². This ensures sufficient tumor to be screened for presence of TIL/TALs, yet it is NOT too restrictive for patients who do not have “sufficiently large” archived tumor specimen for analysis.

- No more than 20% of necrosis is allowed; this ensures that high quality specimens are available for analysis.
- At least 60% of viable melanoma cells are present; this ensures that the melanoma cell compartment is sufficiently larger than the stromal component.
- Must have available archival tissue and subjects must have consented to allow collection of archived tumor blocks from previous surgeries confirming or treating unresectable stage III or distant metastatic disease. If more than one archived tumor block is available, only one block is required to be analyzed for the presence of TIL/TALS. Archived tumor tissues must fulfill the following criteria based on representative H&E-stained tissue sections: (1) the tumor surface area must be $\geq 1\text{cm}^2$ (which can be the sum tumor surface from more than metastatic blocks, if necessary), (2) $\leq 20\%$ of necrosis, (3) the ratio of viable tumor cells to tumor-associated stroma should be $\geq 60/40$, and (4) if TILs are present based on H&E stained sections, they must be $\leq 1\%$ of the total number of cells in the specimen.
- If more than one archived metastatic melanoma specimen is available during the 21-day screening period, only one block is required to be analyzed for the presence of TIL/TALs.

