2.0 STUDY OBJECTIVES

2.1 Primary Objective

Assess the incidence of conversion of non-inflamed (TIL/TAL-absent by histopathologic analysis of H&E-stained tissue section from archived metastatic melanoma tumors) to inflamed melanomas following 3 weeks of entinostat monotherapy by performing histopathologic analysis of representative H&E-stained tissue sections from melanoma tumors before treatment and in the end of cycle 1, beginning of cycle 2 (day 22±2 days), immediately before concurrent pembrolizumab-entinostat treatment on day 22 (±2 days) following single-agent entinostat treatment.

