4.1 Inclusion Criteria

- 4.1.1 Age \geq 18 years at the time of consent.
- 4.1.2 Subject has provided informed consent and HIPAA prior to initiation of any study-specific activities/procedures.
- 4.1.3 ECOG Performance Status of ≤ 2 .
- 4.1.4 Histologically confirmed metastatic (regional or distant) melanoma of any subtype (cutaneous, mucosal, ocular).
- 4.1.5 AJCC stage unresectable III or stage IV disease that is measurable by RECIST v1.1 criteria.
- 4.1.6 Must agree to undergo one on-treatment tumor biopsy on day 22 (± 2 days) of the study. Subjects for whom fresh samples cannot be safely provided (e.g., inaccessible tumor for biopsy) will not be eligible for study participation.
- 4.1.7 Must have available archival tissue and subjects must have consented to allow collection of archived tumor blocks from previous surgeries confirming or treating unresectable stage III or distant metastatic disease. If more than one archived tumor block is available, only one block is required to be analyzed for the presence of TIL/TALS. Archived tumor tissues must fulfill the following criteria based on two representative H&E-stained tissue sections: (1) the tumor surface area must be at least 1cm^2 (which can be from a combination of metastatic blocks if necessary), (2) no more than 20% of necrosis, (3) the ratio of viable tumor cells to tumor-associated stroma should be at least 60/40, and (4) if TILs are present based on H&E stained

sections, they must be $\leq 1\%$ of the total number of cells in the specimen; the amount of tissue should be ≥ 1 cm².

[name], study pathologist, must sign off on the eligibility of archived tumor blocks before study enrollment. If archival tissue is unavailable or insufficient, fresh biopsy should be performed to confirm unresectable stage III or distant metastatic disease.

4.1.8 Previous treatment with immune checkpoint inhibitors and chemotherapies is allowed on condition that the last treatment is at least 28 days prior to first dose of entinostat. Previous treatment with targeted therapies (e.g. MAPK inhibitors) is allowed on condition that the last treatment was administered at least 15 days prior to first dose of entinostat).

4.1.9 Demonstrate adequate organ function as defined in the table below; all screening labs to be obtained within 21 days prior to entinostat treatment.

System	Laboratory Value
Hematological*	

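### Any one archived block, of no stated age and possibly predating later therapy, can set the non-inflamed baseline, so block-to-biopsy differences unrelated to entinostat can count as conversion

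*Combined protocol and SAP*

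**What the plan says.** The primary objective (2.1) is to "Assess the incidence of conversion of non-inflamed (TIL/TAL-absent by histopathologic analysis of H&E-stained tissue section from archived metastatic melanoma tumors) to inflamed melanomas" after three weeks of entinostat alone. Archived tissue therefore does two jobs: it decides eligibility and it is the baseline of the paired comparison.

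The tissue comes from "archived tumor blocks from previous surgeries confirming or treating unresectable stage III or distant metastatic disease" (4.1.7), and "If more than one archived tumor block is available, only one block is required to be analyzed for the presence of TIL/TALS". Section 1.7.1 repeats the one-block allowance. Sections 4.1.7, 1.7.1, 6.3.7 and Appendix C set requirements on area, necrosis, tumor-to-stroma ratio and TIL. None of them limits the block's age, says which block to choose, or refers to treatment given after it was taken.

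A fresh pre-treatment sample is a fallback only: "If archival tissue is unavailable or insufficient, fresh biopsy should be performed to confirm unresectable stage III or distant metastatic disease". The Time and Events table (7.1) schedules a fresh biopsy only at day 22.

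Previous checkpoint inhibitors and chemotherapy are "allowed on condition that the last treatment is at least 28 days prior to first dose of entinostat" (4.1.8). The corresponding interval is 15 days for targeted therapy (4.1.8) and for radiation or major surgery (4.1.12). All are counted to the first entinostat dose.

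Section 5.7.1 requires an accessible, safe lesion at day 22 but not the lesion or site that supplied the block. Under 9.2, any TIL/TAL on that biopsy, brisk or non-brisk, is conversion. At least 3 conversions in 10 evaluable patients is success, with type I error 0.04 at a true rate of 0.08 and power 83% at 0.40.

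**The concern.** With no control arm, the background rate of apparent conversion has to be carried entirely by the null value of 8%. The baseline rules leave several routes to apparent conversion that do not involve entinostat: which block was read, a different metastatic site, elapsed time, and treatment given between block and day 1.

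The plan acknowledges the first two in 1.7.1: "Since the presence of TIL/TALs can be heterogeneous within the same tissue as well as across different metastatic sites". Its response there is a set of sample-quality requirements, which do not deal with site, time or intervening therapy.

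Selection makes the count one-sided. Every patient enters with TIL at or below 1%, so a difference between block and biopsy either counts as conversion or does not register. No opposite event can offset it. The two scales also differ, because a small TIL presence is allowed at entry while any TIL counts at day 22. In addition, 6.3.7 notes that the study pathologist's routine reports already state whether TIL are present. A qualifying block could therefore be picked with its result known.

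At stake is the reading of the only primary question: whether 3 or more conversions reflect entinostat.

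**Working it through.** **Inputs.** From 9.2: n = 10, success at 3 or more, null rate 0.08, alternative 0.40. From 1.1: single arm. The documents give no rate of TIL change between archived block and later biopsy in untreated patients, so the background rates beyond 8% below are assumptions.

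**Formula.** With X ~ Binomial(10, p), P(X ≥ 3) = 1 − [(1−p)^10 + 10p(1−p)^9 + 45p²(1−p)^8].

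**The plan's own figures.**
- p = 0.08: 1 − (0.4344 + 0.3777 + 0.1478) = 0.0401. The plan prints 0.04.
- p = 0.40: 1 − (0.0060 + 0.0403 + 0.1209) = 0.8327. The plan prints 83%.

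Both reproduce.

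**Chance of declaring success with an inert drug, by background rate.**

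| Background p | P(X ≥ 3) |
|---|---|
| 0.08 (plan) | 0.040 |
| 0.10 | 0.070 |
| 0.15 | 0.180 |
| 0.20 | 0.322 |
| 0.25 | 0.474 |
| 0.30 | 0.617 |

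Solving P(X ≥ 3) = 0.05 gives p = 0.087. The margin above the plan's null is 8.7 − 8.0 = 0.7 percentage points.

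**Could the threshold be raised instead?** At 10 patients the smallest cut-off with type I error within 5% is:
- background 15%: at least 4 of 10 (type I error 0.050, power 62% at 0.40);
- background 20%: at least 5 of 10 (type I error 0.033, power 37%).

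Keeping 80% power against 0.40 would need 22 patients (at least 7) at 15%, or 35 patients (at least 12) at 20%. Raising the threshold is therefore no practical repair at this size. The background has to be kept low and made visible.

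**Do the eligibility rules bound the background?** The disease-setting rule restricts tissue to unresectable stage III or distant disease. It does not restrict date or prior therapy. The washouts restrict therapy relative to dose 1. A block taken before a checkpoint inhibitor that ended 28 days before dose 1 satisfies every criterion. Nothing in 4.1.7, 1.7.1, 6.3.7 or Appendix C excludes it or asks that the sequence be recorded.

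**The case against.** **Direction is not established.** A reader might infer that earlier checkpoint inhibitors, targeted therapy or radiation bring TIL into lesions and so manufacture conversions. No section says so; 1.2.2 says only that TIL already present are associated with response. Section 1.3 does say "Cancer immunogenicity and antigenicity is a complex phenomenon that dynamically changes as cancers develop, establish and progress", but it goes on to describe immunoediting that may remove immunoreactive clones and leave the others to grow. On that account a current lesion may be less inflamed than an old block, which would lower apparent conversion. A day-22 core or punch may also sample less tissue than the 1 cm² required of the archive. These points stand: the route to bias exists, but its net size and sign over time are unknown.

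**Some background is allowed for.** The 8% null is not zero, and nothing in the documents shows that the true rate is higher. That also stands, but no basis for 8% is given and the margin is small.

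**Known inflamed blocks are barred.** A reader might infer that a patient with one inflamed and one non-inflamed block always qualifies. The Appendix C letter attests that none of the slides reviewed shows 1% or more TIL/TAL, so such a patient qualifies only if the inflamed block is not reviewed. Since one block suffices, the letter narrows the gap without closing it.

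**The trial is exploratory.** It has 10 to 12 evaluable patients, and blood samples on days 1 and 22 give a contemporaneous check. This tempers the severity. The blood samples do not measure tumor TIL, however, and the plan still states a success rule with type I error and power.

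**Conclusion.** The concern holds as a weakness in attribution that should be fixed. The printed type I error and power are arithmetically right. They describe the entinostat question only if apparent conversion without a drug effect is about 8%, and at most about 8.7% for a 5% error. The baseline rules do little to secure that, and the plan does not justify it. At assumed backgrounds of 10%, 15%, 20% and 30%, false success is 7%, 18%, 32% and 62%; none of these rates comes from the documents.

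The stronger conclusion, that 3 of 10 cannot be read as an entinostat effect at all, is not supported. It would need evidence that the true background exceeds the null, and the documents contain none. Patients with no adequate archive have a fresh biopsy, so the problem does not reach everyone.

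**What to change.** 1. **Baseline block.** In 4.1.7 and 1.7.1, replace the one-block allowance with a rule that the most recent adequate metastatic block is read for eligibility and used as baseline. When blocks are otherwise equivalent, choose the one from the site to be biopsied on day 22. Carry the same rule into 6.3.7 and the Appendix C letter.
2. **Records.** Capture block date, block site, day-22 biopsy site, and any systemic therapy or radiation between block and day 1.
3. **Analysis (9.2).** Keep at least 3 of 10 as the primary rule. Add descriptive conversion counts with exact 95% confidence intervals for patients whose baseline block post-dates their last anticancer therapy and for those whose block does not. State that attribution to entinostat depends on the assumed 8% background.

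The subgroup counts should stay descriptive. If 5 of 10 patients had a post-therapy block (an assumption), at least 2 of 5 would have type I error 5.4% at 0.08 and power 66% at 0.40; at least 3 of 5 would have 0.5% and 32%. Neither is a usable decision rule. Excluding patients for any inflamed older block is not proposed, because it would cost accrual.

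**Cost.** Protocol wording, a few data fields and reading of existing slides, with no added biopsy. A few patients whose most recent block is inflamed become ineligible, and the subgroup counts will be small. Site differences are reduced but not removed, since the earlier lesion may have been resected or, if in the lung, is not to be biopsied under 5.7.1.

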Hemoglobin (Hgb)	≥ 9 g/dL or ≥ 5.6 mmol/L without transfusion or erythropoietin dependency (within 7 days of assessment of Hgb)
Absolute Neutrophil Count (ANC)	$\geq 1,500/\text{mm}^3$
Platelets	$\geq 100,000/\text{mm}^3$
Renal*	
Creatinine	≤ 1.5 x upper limits of normal (ULN) OR
Measured or calculated ¹ creatinine clearance (CrCl) (glomerular filtration rate [GFR] can also be used in place of creatinine of CrCl)	≥ 60 mL/min using the Cockcroft-Gault formula for subjects with creatinine levels > 1.5 x institutional ULN
Hepatic*	
Bilirubin	≤ 1.5 xULN OR Direct bilirubin \leq ULN for patients with total bilirubin levels >1.5 xULN
Aspartate aminotransferase (AST)	≤ 2.5 xULN OR < 5 xULN for subjects with liver metastases
Alanine aminotransferase (ALT)	≤ 2.5 xULN OR < 5 xULN for subjects with liver metastases
Albumin	≥ 2.5 mg/dL
Coagulation*	

System	Laboratory Value
International Normalized Ratio (INR) or Prothrombin Time (PT)	≤1.5xULN, unless subject is receiving anticoagulant therapy as long as PT or PTT is within therapeutic range of intended use of anticoagulants
Activated Partial Thromboplastin Time (aPTT)	≤1.5xULN, unless subject is receiving anticoagulant therapy, as long as PT or PTT is within therapeutic range of intended use of anticoagulants

*Note: Hematology and other lab parameters that are ≤ grade 2 BUT still meet criteria for study entry are allowed. Furthermore, changes in laboratory parameters during the study should not be considered AEs unless they meet criteria for dose modification(s) of study medication outlined by the protocol in Section 5.3.1 and/or worsen from baseline during therapy.

4.1.10 A female of childbearing potential must have a negative serum pregnancy test during screening and a negative urine pregnancy test within 3 days prior to receiving the first dose of study drug. If the screening serum test is done within 3 days prior to receiving the first dose of study drug, a urine test is not required. A female of childbearing potential must agree to use effective contraception during the study and for 120 days after the last dose of study drug. A female of non-childbearing potential defined as (by other than medical reasons):

- ≥45 years of age and has not had menses for >2 years,
- Amenorrheic for <2 years without a hysterectomy and oophorectomy and a follicle-stimulating hormone value in the postmenopausal range upon pre-study (screening) evaluation,

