- Post hysterectomy, oophorectomy or tubal ligation. Documented hysterectomy or oophorectomy must be confirmed with medical records of the actual procedure or confirmed by an ultrasound. Tubal ligation must be confirmed with medical records of the actual procedure; otherwise the patient must be willing to use 2 adequate barrier methods throughout the study, starting with the screening visit through 120 days after the last dose of entinostat,
- If male, agrees to use an adequate method of contraception starting with the first dose of study drug through 120 days after the last dose of entinostat,
- See section 5.6.2 for information on acceptable methods of contraception.

4.1.11 Experienced resolution of toxic effect(s) of the most recent prior anti-cancer therapy to Grade ≤1 (except alopecia or neuropathy) by CTCAE v5.0. Exceptions

are patients who may have developed autoimmune-type side effects that require permanent hormonal replacement from previous therapies.

- 4.1.12 If the patient underwent major surgery or radiation therapy, these procedures must have occurred at least 15 days prior to the first dose of entinostat. In addition, patients must have recovered from the toxicity and/or complications from the intervention to Grade ≤ 1 .
- 4.1.13 Subjects must be willing and able to comply with study procedures based on the judgement of the investigator or protocol designee.

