4.2 Exclusion Criteria

All subjects meeting any of the exclusion criteria at baseline will be excluded from study.

- 4.2.1 Is receiving systemic steroid therapy or any other form of immunosuppressive therapy for autoimmune side effects related to previous use of immunotherapies for melanoma. Exceptions include episodic (up to 7 days) use of systemic steroids for common conditions while on study treatment (e.g. COPD exacerbation, poison ivy), use of corticosteroids as replacement doses for adrenal or pituitary insufficiency.
- 4.2.2 Has a known history of tuberculosis (Bacillus Tuberculosis) or human immunodeficiency virus (HIV 1/2 antibodies).
- 4.2.3 Hypersensitivity to pembrolizumab or any of its excipients. Allergy to benzamide or inactive components of entinostat.
- 4.2.4 Has known history of biopsy-proven (non-infectious) pneumonitis that required systemic steroids, or any evidence of current pneumonitis.
- 4.2.5 Conditions that would preclude adequate absorption of oral medications (malabsorption, significant nausea and vomiting, resection of >100 -cm of proximal small bowel, resection of >200 -cm of distant small bowel).
- 4.2.6 Has a history or current evidence of any condition, therapy, or laboratory abnormality that might confound the results of the trial, interfere with the subject's participation for the full duration of the trial, or is not in the best interest of the subject to participate, in the opinion of the treating investigator, including but not limited to:
- i.** Myocardial infarction or arterial thromboembolic events within 6 months prior to screening or severe or unstable angina, New York Heart Association (NYHA) Class III or IV disease, or a QTc interval > 470 msec,
 - ii.** Active infection requiring systemic antibiotic therapy by the first day of entinostat treatment,
 - iii.** Known psychiatric or substance abuse disorders that would interfere with cooperation with the requirements of the trial.

- 4.2.7 If female, is pregnant or breastfeeding, or, if male, expecting to conceive or father children within the projected duration of the trial, starting with the pre-screening or screening visit through 120 days after the last dose of trial treatment.

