5.0 TREATMENT PLAN

5.1 Schema

Eligible subjects must have histologically confirmed AJCC stage III/IV melanoma of any subtype and sufficient, archived metastatic tumor tissue to confirm absence

of TIL/TAL in representative H&E-stained tumor tissues. Subjects are eligible even if they have received any prior PD-1/PD-L1 pathway inhibitors or any other systemic treatments, including immunotherapies, on condition that they have not received HDACi for their melanoma. They must have recovered from any side effects associated with prior anticancer treatments. Patients will be 'primed' with entinostat, 5mg PO qwk, for 3 weeks. In the end of cycle 1, beginning of cycle 2 (day 22±2 days), immediately before concurrent entinostat-pembrolizumab treatment, they will undergo a mandatory melanoma biopsy after which they will receive up to 4 infusions of standard of care pembrolizumab along with weekly administration of entinostat. Restaging radiographic studies will be performed on week 10 and then every 6 weeks until week 27. Peripheral blood will be collected at baseline; in the end of cycle 1, beginning of cycle 2 (day 22±2 days), immediately before concurrent entinostat-pembrolizumab treatment; on week 10 after 3 infusions (cycles) of pembrolizumab; and at the end of treatment, either at disease progression or week 27, or if intolerable toxicity occurs that requires permanent discontinuation of pembrolizumab and/or entinostat. Subjects will be considered to have completed all trial requirements if:

- (a) Their disease has progressed by RECIST v1.1 criteria within less than 10 weeks from the first dose of entinostat,
- (b) They develop toxicity related to pembrolizumab or entinostat, but still complete sample collection (peripheral blood and tumor tissue) and tumor assessments by at least week 3,
- (c) Complete the entire 27 weeks of combination therapy and study-related assessments without experiencing disease progression by RECIST v1.1 criteria or clinical grounds. Those subjects experiencing clinical benefit after 27 weeks may continue pembrolizumab therapy per standard of care.

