Dosing interruptions are permitted in the case of medical/surgical events or logistical reasons not related to study therapy (e.g., elective surgery, radiation therapy, unrelated medical events, patient vacation, and/or holidays). Subjects should be placed back on study therapy within 3 weeks (i.e., 21 days) of the scheduled interruption, unless otherwise discussed with the Sponsor. The reason for interruption should be documented in the patient's study record. If pembrolizumab is permanently discontinued, entinostat must be discontinued as well.

Attribution of Toxicity:

When study interventions are administered in combination, attribution of an adverse event to a single component is likely to be difficult. Therefore, while the investigator may attribute a toxicity event to the combination, to entinostat alone or to pembrolizumab alone], for adverse events listed in the table below, both interventions must be held according to the criteria in the table below: Dose Modification and Toxicity Management Guidelines for Immune-Related Adverse Events Associated with Pembrolizumab and IO Combinations.

Holding Study Interventions:

When study interventions are administered in combination, if the AE is considered immune-related, both interventions should be held according to recommended dose modifications.

Restarting Study Interventions:

Participants may not have any dose modifications (no change in dose or schedule) of pembrolizumab in this study, as described in the table below.

- If the toxicity does not resolve or the criteria for resuming treatment are not met, the participant must be discontinued from all study interventions.
- If the toxicities do resolve and conditions are aligned with what is defined in the table below, the combination of entinostat and pembrolizumab may be restarted at the discretion of the investigator. In these cases where the toxicity is attributed to the combination or to entinostat alone, re-initiation of pembrolizumab as a monotherapy may be considered at the principal investigator's discretion.

Dose modification and toxicity management guidelines for immune-related AEs associated with pembrolizumab monotherapy and IO Combinations

General instructions:

1. Severe and life-threatening irAEs should be treated with IV corticosteroids followed by oral steroids. Other immunosuppressive treatment should begin if the irAEs are not controlled by corticosteroids.

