6.2 Pembrolizumab (Keytruda™) - Commercial Drug

6.2.1 Description

Pembrolizumab is a humanized monoclonal antibody that blocks the interaction between PD-1 and its ligands, PD-L1 and PD-L2. Pembrolizumab is an IgG4κ immunoglobulin with an approximate molecular weight of 140 kD. Full prescribing information for pembrolizumab is available at:

http://www.merck.com/product/usa/pi_circulars/k/keytruda/keytruda_pi.pdf

6.2.2 **Dosage and Administration:**

Pembrolizumab (200 mg) will be administered IV over 30 min (range of infusion time, 25-40 min) every 21 days (i.e., three weeks) in combination with entinostat. Pembrolizumab should be given on D1 of each cycle, except for cycle 1, after entinostat dosing occurs assuming patient is not on a hold for entinostat.

6.2.3 **Storage and Stability:**

Solution for infusion vials should be stored at refrigerated conditions (2–8 °C) and protected from light.

Clinical supplies must be stored in a secure, limited-access location under the storage conditions specified on the label. Receipt and dispensing of trial medication must be recorded by an authorized person at the trial site.

Handling and Disposal: Local requirements for disposal of hazardous drugs should be followed at each participating clinical site.

Please see UNC policy on hazardous drugs:

<http://intranet.unchealthcare.org/intranet/hospitaldepartments/safetynet/policies/hazardousdrugs.pdf>

6.2.4 **Adverse Events Associated with Commercial Drug**

The most common AEs (reported in $\geq 20\%$ of patients in clinical trials of pembrolizumab) included fatigue, pruritus, diarrhea, decreased appetite, rash, pyrexia, cough, dyspnea, musculoskeletal pain, constipation, and nausea. The following warnings are associated with the use of pembrolizumab:

Immune-Mediated Pneumonitis

Pneumonitis occurred in $\sim 3\%$ of melanoma patients treated in clinical trials of pembrolizumab. The median time-to-development of pneumonitis was 5 months with a median duration of 4.9 months. The one patient with Grade 3 pneumonitis required initial treatment with high-dose systemic corticosteroids (greater than or equal to 40 mg prednisone or equivalent per day) followed by a corticosteroid taper. Pneumonitis completely resolved in seven of the nine patients with Grade 2-3 pneumonitis.

Immune-Mediated Colitis

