Hyperthyroidism occurred in 5 (1.2%) of 411 melanoma patients treated in clinical trials of pembrolizumab. The median time-to-onset was 1.5 months and the median duration was 2.8 months (range 0.9 to 6.1 months). One of two patients with Grade 2 and the one patient with Grade 3 hyperthyroidism required initial treatment with high-dose corticosteroids (greater than or equal to 40 mg prednisone or equivalent per day) followed by a corticosteroid taper. One patient required permanent discontinuation of pembrolizumab due to hyperthyroidism. All five patients with hyperthyroidism experienced complete resolution of the event.

Immune-Mediated Hypothyroidism

Hypothyroidism occurred in 34 (8.3%) of 411 melanoma patients treated in clinical trials of pembrolizumab. The median time-to-onset of hypothyroidism was 3.5 months. All but two of the patients with hypothyroidism were treated with long-term thyroid hormone replacement therapy. The other two patients only required short-term thyroid hormone replacement therapy. No patient received corticosteroids or discontinued pembrolizumab for management of hypothyroidism. Thyroid disorders can occur at any time during treatment.

Other Immune-Mediated Adverse Reactions

Other clinically important immune-mediated adverse reactions can occur. The following clinically significant, immune-mediated adverse reactions occurred in less than 1% of patients treated with pembrolizumab, including exfoliative dermatitis, uveitis, arthritis, myositis, pancreatitis, hemolytic anemia, partial seizures arising in a patient with inflammatory foci in brain parenchyma, and adrenal insufficiency.

Across clinical studies with pembrolizumab in approximately 2,000 patients, the following additional clinically significant, immune-mediated adverse reactions were reported in less than 1% of patients: myasthenic syndrome, optic neuritis, and rhabdomyolysis.

Embryofetal Toxicity

Pembrolizumab may cause fetal harm when administered to a pregnant woman. Animal models link the PD-1/PD-L1 signaling pathway with maintenance of pregnancy through induction of maternal immune tolerance to fetal tissue.

Steven's Johnson Syndrome (SJS) and Toxic Epidermal Necrolysis (TEN)

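### Section 4.1.10 counts 120 days of contraception from the last entinostat dose for two groups, so cover after pembrolizumab can fall below 120 days if pembrolizumab is the last drug given on study

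*Combined protocol and SAP*

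**What the plan says.** Section 4.1.10 sets the end of contraception in three places.

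- A woman of childbearing potential "must agree to use effective contraception during the study and for 120 days after the last dose of study drug".
- A woman whose tubal ligation is not confirmed from medical records uses two barrier methods "throughout the study, starting with the screening visit through 120 days after the last dose of entinostat".
- A man uses an adequate method "starting with the first dose of study drug through 120 days after the last dose of entinostat".

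Exclusion 4.2.7, which covers pregnancy, breastfeeding and men expecting to father children, runs "through 120 days after the last dose of trial treatment".

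On the order in which the drugs stop, sections 5.3, 5.3.2 and 5.3.3 say that entinostat must stop when pembrolizumab is permanently discontinued. No section states the converse. Where toxicity is attributed to the combination or to entinostat alone, section 5.3.2 says that "re-initiation of pembrolizumab as a monotherapy may be considered", at the principal investigator's discretion. Section 6.2.2 has pembrolizumab given on day 1 of each cycle from cycle 2, "after entinostat dosing occurs assuming patient is not on a hold for entinostat".

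**The concern.** Two of the three contraception rules in 4.1.10 name only one of the two study drugs. If entinostat is the last drug given, this does no harm. If pembrolizumab is last, the 120 days have already started to run before its final dose.

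The stake is clearest for the tubal-ligation group. These women are asked for barrier methods because sterility is not documented, and section 6.2.4 states: "Pembrolizumab may cause fetal harm when administered to a pregnant woman". Their written end date takes no account of that drug.

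For men the point is one of consistency with 4.2.7 only. The reproductive findings in section 1.4.6.1 (reduced fertility and teratogenicity in animals) concern entinostat, and the documents state no risk from a father's exposure to pembrolizumab.

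**Working it through.** **Inputs.** Contraception period: 120 days after the last entinostat dose (4.1.10). Dosing days from the schema in 5.2.1: last scheduled entinostat D183, last scheduled pembrolizumab D169.

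**Formula.** Days of cover after the last pembrolizumab dose = (last entinostat day + 120) − last pembrolizumab day. Cover is below 120 exactly when the last entinostat dose comes before the last pembrolizumab dose, and the shortfall equals the gap between them.

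**Full schedule.** 183 + 120 = D303, and 303 − 169 = 134 days. A period counted from pembrolizumab would end on 169 + 120 = D289, so the present rule has 303 − 289 = 14 days to spare.

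**Entinostat held at the D169 visit and not resumed; pembrolizumab given.** Last entinostat is D162. 162 + 120 = D282, 282 − 169 = 113 days, and 120 − 113 = 7 days short. This fits the rule in 5.3.1 that ends entinostat when more than half the doses in any six weeks are missed. Of the six doses from D148 to D183, three are missed (D169, D176, D183), which is 50% and not more.

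**A longer hold that still covers the D169 infusion.** Last entinostat D155: 155 + 120 − 169 = 106 days, 14 short. Last entinostat D148: 148 + 120 − 169 = 99 days, 21 short. In the second case three of the six doses from D134 to D169 are missed by the infusion, again 50%.

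**Pembrolizumab restarted alone under 5.3.2.** The documents set no timetable, so no figure is given. The shortfall is whatever gap results, and it may exceed a week where a steroid taper comes first.

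**With the later of the two doses as the starting point.** Cover after the last pembrolizumab dose is at least 120 days in every case, and the full-schedule end date stays at D303.

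**The case against.** **The tubal-ligation group may already be covered.** A woman without records has not met the definition of non-childbearing potential, so the general rule for women of childbearing potential can be read as applying to her as well. That is a fair reading. It does not remove the specific bullet with its own end date, and it helps only if *study drug* in the general rule includes pembrolizumab. The protocol is not consistent on this: 5.3.1 uses the term for entinostat, 6.4.5 equates the first dose of study drug with the first entinostat dose, and the infusion-reaction table in 5.6.1 uses it for pembrolizumab. The contrast within 4.1.10 is therefore less secure than it looks. The same ambiguity means that mending the tubal-ligation bullet alone would be incomplete.

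**The words *throughout the study*.** These cover on-study dosing for the tubal-ligation group, so only the time after treatment is in question. Follow-up runs to two years, but the phrase goes on to give its own end date.

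**The route is narrow.** Section 5.1 lists as an end-of-treatment trigger for blood sampling the case "if intolerable toxicity occurs that requires permanent discontinuation of pembrolizumab and/or entinostat", which suggests that treatment often ends when entinostat does. That sentence sets sampling times. It does not withdraw the permission in 5.3.2.

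**No pembrolizumab benchmark.** The only stated basis for 120 days is note b in 5.6.2, which combines elimination time with 30 days for genotoxic potential and is itself counted from entinostat. This stands: the shortfalls measure inconsistent wording, not a demonstrated exposure risk.

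**Stronger readings.** A reader might infer a 28-day gap from last entinostat on D141 with pembrolizumab alone on D148 and D169 (141 + 120 − 169 = 92 days). That timetable is unlikely. Four of the six entinostat doses from D134 to D169 would be missed (67%). Entinostat is due before the infusion, so the 5.3.1 threshold would be passed before the D169 infusion, and 5.1 points to end of treatment for permanent discontinuation due to toxicity. A restart alone on D148, 7 days after the last entinostat dose, also sits badly with the steroid taper of at least four weeks in 5.3.2 where steroids are used. A reader might also infer a documented hazard for partners of male participants. The documents contain none.

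**Conclusion.** The point holds as a minor, conditional defect in safety wording. As written, the rule gives less than 120 days after pembrolizumab whenever pembrolizumab is the last drug given on study, and the protocol permits that order. In the worked example the shortfall is 7 days (113 instead of 120). It is 14 or 21 days if the hold before the final infusion is longer. On the full schedule there is none.

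This rests on two assumptions: that 120 days is meant to apply to both drugs, as 4.2.7 implies, and that the bullet's stated end date is what sites would follow. The stop dates are illustrations. The documents give no frequency for entinostat stopping first, and planned enrolment is only 14 (section 9.2), so the number affected may be zero. They do not support a claim that participants on the planned schedule are under-protected. No endpoint, sample size or analysis changes.

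**What to change.** Use one end date in 4.1.10: *120 days after the last on-study dose of entinostat or pembrolizumab, whichever is later*. Put it in the tubal-ligation bullet and in the sentence for women of childbearing potential, where *study drug* is ambiguous. Align the male bullet with 4.2.7 for consistency only. The words *on-study* keep later standard-of-care pembrolizumab out of the requirement. Check that the consent form, which was not available for this review, says the same.

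The cost is a few words in one criterion and a consent-form check. The downside is a somewhat longer contraception period for the few participants who stop entinostat first. For everyone completing the schedule the end date remains D303.
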